ATTACHMENT 1: PREDEFINED MAJOR PROTOCOL DEVIATIONS-BASED ON THE CURRENT LIST

The predefined major protocol deviations of this study are described in the Protocol Deviation Criteria document. The deviations that are considered to have an (possible) impact on efficacy are a subset of the predefined major protocol deviations and are indicated with 'Yes' below (column 'Exclude from Per Protocol Analysis') and if such deviations are reported for a subject, the subject will be excluded from the PP analysis.

In addition to the table below, subjects with a baseline HIV-1 RNA value ≥ 50 copies/mL and subjects with treatment adherence $< 65\%$ (Late Switch group will use worst adherence from baseline to switch and from switch to week 96) per derivation ii will also be excluded from the per-protocol analysis set.

Sequence No.	Description	Protocol Deviation coded term (DVDECOD)	Exclude from PP
1	The subject has not been treated with a stable ARV regimen consisting of a bPI (limited to DRV or ATV with rtv or COBI, or LPV with rtv) combined with FTC/TDF only for at least 6 consecutive months preceding the screening visit.	Entered but did not satisfy criteria	Yes
2	
 • During the 12 months preceding screening while on stable ART: 
 - The subject did not have at least 1 plasma HIV-1 RNA measurement < 50 copies/mL (or HIV-1 RNA undetectable by a local HIV-1 RNA test) occurring between 12 and 2 months prior to the screening visit while on the stable ARV regimen or - The subject has a documented plasma HIV-1 RNA concentrations ≥ 200 copies/mL. or - The subject has documented more than 1 plasma HIV-1 RNA concentrations ≥ 50 copies/mL (or HIV-1 RNA detectable by a local 	Entered but did not satisfy criteria	Yes

	
HIV-1 RNA test)
 
or
 
 - The subject has at least 1 single documented plasma HIV-1 RNA concentrations ≥ 50 copies/mL and < 200 copies/mL but had no subsequent VL measurement < 50 HIV-1 RNA copies/mL at the latest 2 months prior to screening 
or
 
 • At the screening visit has HIV-1 RNA ≥ 50 copies/mL. 		
3	The subject has a history of failure on DRV treatment or any of DRV RAMs (V11I, V32I, L33F, I47V, I50V, I54M, I54L, T74P, L76V, I84V, L89V) (if historical genotypes are available)	Entered but did not satisfy criteria	Yes
4	The subject uses disallowed concomitant therapy specified in the protocol	Entered but did not satisfy criteria	Yes
5	The subject has any known allergies to the excipients of the D/C/F/TAF tablet, but the subject was randomized.	Entered but did not satisfy criteria	Yes

6	The dose of Investigational treatment arm (D/C/F/TAF tablet) or the active control arm (maintain current regimen consisting of a bPI with FTC/TDF) was temporarily not according to protocol for more than 4 consecutive weeks.	Received wrong treatment or incorrect dose (missed dose or extra dose)	Based on >4 weeks period. In that case classified as major and excluded from PP
7	The intake of Investigational treatment arm (D/C/F/TAF tablet) or the active control arm (maintain current regimen consisting of a bPI with FTC/TDF) was interrupted for toxicity reasons for more than 4 consecutive weeks.	Received wrong treatment or incorrect dose (missed dose or extra dose)	
8	The intake of Investigational treatment arm (D/C/F/TAF tablet) or the active control arm (maintain current regimen consisting of a bPI with FTC/TDF) was interrupted for non-toxicity reasons for more than 4 consecutive weeks, or cumulatively for more than 8 weeks.	Received wrong treatment or incorrect dose (missed dose or extra dose)	
9	The subject takes disallowed medication as defined per protocol.	Received a disallowed concomitant treatment	Yes (adjudication based on drug/class and duration).
10	The subject missed two or more consecutive planned visits in the trial	Other	Yes
11	Misallocation of Medkits was observed during Dosage and administration of study drug and subject treated differently than what they were randomized to for more than 4 weeks	Other	Yes
12	After achieving HIV-1 RNA <50 copies/mL, a single HIV-1 RNA value was ≥ 50 copies/mL, but a viral load retest or scheduled viral load test within 6 weeks of the previous VL result of ≥ 50 copies/mL was not collected (except for screening and baseline results)	Other	Yes
13	Subject missed the Week 96 visit.	Other	Yes
*Some sites assumed that protocol language “abnormal lab values that would lead to exclusion could be repeated once” applied also to viral load >50c/mL at screening.			

** Including subjects whose HIV-1 RNA was ≥ 50 copies/mL at screening, but had a HIV-1 RNA < 50 copies/mL at a not per protocol defined retest during the screening period and who were randomized based on the latter HIV-1 RNA.

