2.7. Definition of Subgroups

2.7.1. Subgroups for Efficacy Analyses

- Adherence based on D/C/F/TAF (i.e., from reference) drug accountability (>95%: adherent, $\leq 95\%$: non-adherent, missing/unknown)
- Reference viral load
 - For Initial D/C/F/TAF group the screening and baseline viral load
 - <50; if all screening and baseline viral load values are below 50 copies/mL
 - ≥ 50 ; if at least one viral load value during screening or baseline ≥ 50 copies/mL)
 - For Late Switch group, the reference viral load
 - <50 copies/mL
 - ≥ 50 copies/mL
- CD4+ count at reference (<200, ≥ 200 [200 $\leq x < 350$, 350 $\leq x \leq 500$, >500] cells/mm³)
- Race (American Indian or Alaska Native, Asian, Black or African American, White, Native Hawaiian or other Pacific Islander, Other, non-Black or African American)
- Ethnicity (Hispanic or Latino, non-Hispanic or Latino)
- Gender (Female, Male)
- Age group (≤ 50 , >50 years)
- Region (Europe, North America)
- Re-classified bPI at screening (see section 2.5):
 - DRV once daily with rtv or COBI; ATV with rtv or COBI; LPV with rtv
 - ATV with rtv or COBI, or LPV with rtv
 - DRV with rtv; DRV with COBI
- Booster at screening (ritonavir or cobicistat)
- Number of previous ARVs used (3, 4, 5, 6, 7, >7) and previous PI, N(t)RTI or NNRTI used (0, 1, 2, 3, 4, >4)

- Previous ARV failure and previous PI, N(t)RTI or NNRTI failure (0, ≥ 1)
- WHO Clinical Staging of HIV/AIDS
- Viral blip (see section 4.6.1) during first 48 weeks:
 - Yes, if subject experience at least 1 viral blip during the first 48 weeks of the study
 - No, otherwise
- For the Late Switch group only:
 - Protocol-defined virologic rebound during first 48 weeks
 - Yes, if subject experience a protocol-defined virologic rebound during the first 48 weeks of the study
 - No, otherwise

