2.9. Reference

For Initial D/C/F/TAF group, reference is the comparative treatment phase baseline as in Week 48 analysis. For the late switch group two references will be used: (1) comparative treatment baseline will be used as reference for the period up to the switch; (2) the last value prior to the switch will be used as reference for the extended treatment phase.

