3.6. Treatment Adherence

Treatment adherence based on drug accountability will be summarized by means of descriptive statistics and frequency tabulations. Cumulative treatment adherence will be calculated from baseline through Week 96 for the Initial Switch to D/C/F/TAF arm; from baseline to the switch, and again from the switch to Week 96 for the Late Switch to D/C/F/TAF arm. Cumulative treatment adherence will be determined (derivation i).

The following parameters are derived:

Amount to be taken through switch/Week 96 = (number of days since start of treatment/switch \times number of tablets to be taken per day).

Number of days since start of treatmentswitch is based on (whichever comes sooner):

- last study medication intake (if available) or, in case subject discontinued and last study medication intake is missing, the last visit date prior to withdrawal will be used.
- Switch/Week 96 visit date

In addition (derivation ii), the cumulative treatment adherence up to time point where not more than one bottle is missing, or if available, up to switch/Week 96, whichever comes sooner, will be calculated.

Actual amount taken = (number of tablets dispensed – number of tablets returned), summed over time points up to the time point of interest.

Level of adherence = (actual amount taken / amount to be taken) × 100%

Treatment adherence is defined as:

- adherent: the level of adherence is >95%,
- non-adherent: the level of adherence is ≤95%.

Additionally, following categories of level of adherence will be defined:

- >95%
-]80%; 95%]
-]65%; 80%]
-]50%; 65%]
- ≤ 50%

Interruptions (for AEs) are not to be taken into account for the calculation of adherence, i.e. they will not be subtracted from the amount to be taken.

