4.4.2.1. Data Handling for Late Switchers

Except for analyses by analysis time point or change from baseline, data (i.e., Protocol-defined virologic rebound through Week96, Snapshot at Week 96, TLOVR and Resistance analyses) from the Late Switch to D/C/F/TAF group will be presented in tables and figures from the reference onwards to Week 96.

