4.6.2. Analysis Methods

Protocol-defined virologic rebound, Snapshot and TLOVR approach

Tabulations (numbers and proportions) per time point will be provided for the Snapshot outcomes (success, failure, no data within window). Tabulations (numbers and proportions) will also be provided for the categorical parameters (virologic rebounders and TLOVR), through Week 96. The exact 2-sided 95% CIs around in each treatment group will be calculated by the Clopper-Pearson method for Protocol-defined virologic rebound, Snapshot virologic success and virologic failure, and TLOVR response. Bar charts will be presented for virologic rebounders and Snapshot outcomes.

Time to virologic rebound

Time to virologic rebound will be graphically presented by means of Kaplan-Meier curves and a Cox proportional hazards model will be fit separately for each treatment group. Terms included in the model for the initial D/C/F/TAF group will be bPI at screening, and any pre-dose (screening phase) viral load ≥ 50 copies/mL (Yes/No). Terms in the model for the Late Switch group will be bPI at screening and any pre-D/C/F/TAF dose viral load ≥ 50 copies/mL (Yes/No).

Immunologic Change

Descriptive statistics (n, mean (se), median, and ranges) per time point will be provided for the continuous parameters, CD4 cell count actual values and change from reference. CIs for the means and mean changes will be calculated. The changes from reference (NC=F) of the two treatment arms and the 95% CIs at Week 96 will be constructed using ANCOVA separately for each treatment group, including term for bPI at screening and reference CD4+ value as a covariate. A sensitivity analysis using Mixed-effects model for repeated measures (MMRM) approach will also be performed separately for each treatment. The model will include change from reference as a response variable (observed case), terms for bPI at screening, visit, and the corresponding reference value as a covariate. An unstructured covariance matrix will be used to model the correlation among repeated measurements.

Cross-tabulations of Week 96 CD4 cell count versus reference will be provided using the categories: < 200 , $200 \leq x < 350$, $350 \leq x \leq 500$, > 500 cells/mm³

Viral Blip

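### The per-protocol RNA exclusion for late switchers is applied at study baseline, about 52 weeks before they start D/C/F/TAF, instead of at their pre-switch reference

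*SAP*

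**What the plan says.** SAP 2.6.2 defines the per-protocol set as the ITT set less subjects with the major deviations in Attachment 1. Above its table, Attachment 1 adds two exclusions in one sentence. The first removes "subjects with a baseline HIV-1 RNA value" of 50 copies/mL or more. The second removes subjects with adherence below 65%, and it alone has a late-switch rule: "Late Switch group will use worst adherence from baseline to switch and from switch to week 96".

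Elsewhere the SAP gives late switchers their own starting point:

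- SAP 2.9: "the last value prior to the switch will be used as reference for the extended treatment phase".
- SAP 4.4.2.1: rebound, Snapshot, TLOVR and resistance data "from the Late Switch to D/C/F/TAF group will be presented in tables and figures from the reference onwards to Week 96".
- SAP 2.7.1, viral-load subgroup: "For Late Switch group, the reference viral load", split at 50 copies/mL.
- SAP 4.6.2, time to rebound: "Terms in the model for the Late Switch group will be bPI at screening and any pre-D/C/F/TAF dose viral load" of 50 copies/mL or more.

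Protocol 11.3 also words the per-protocol RNA condition in terms of baseline. The Amendment 4 rationale explains it: the study asks whether D/C/F/TAF maintains suppression in people already suppressed when they start it, and subjects at 50 or more at that point are not the population of interest.

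**The concern.** For initial switchers, Day 1 is both study baseline and the start of D/C/F/TAF, so the exclusion does what the rationale asks. Late switchers start D/C/F/TAF at the Week 52 switch visit. For them the same words test a value taken about a year before the regimen under assessment begins and before the outcome window opens. The per-protocol set therefore selects on different grounds in the two groups. In the late-switch group, viraemia that arose on the earlier boosted-PI regimen can remain in the set and be counted as rebound on D/C/F/TAF. What is at stake is the meaning of the late-switch per-protocol estimates as a robustness check.

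**Working it through.** No figure in the plan is in dispute, so the check is a comparison of rules followed by an illustration of size.

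**1. What baseline means in Attachment 1.** The adherence rule in the same sentence speaks of a period running from baseline to the switch, so baseline cannot be the switch. SAP 2.9 has a separate term, reference, for the last pre-switch value. Baseline is therefore study Day 1.

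**2. The rules side by side.**

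| Item | Initial switchers | Late switchers |
|---|---|---|
| D/C/F/TAF starts | Day 1 | Week 52 switch |
| Efficacy counted from (SAP 2.9, 4.4.2.1) | Day 1 baseline | last value before the switch |
| Viral-load subgroup (SAP 2.7.1) | screening and baseline | reference |
| Cox viral-load term (SAP 4.6.2) | before first dose | before first D/C/F/TAF dose |
| Per-protocol RNA exclusion (Attachment 1) | Day 1 | Day 1 |

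Only the last row fails to follow the start of D/C/F/TAF.

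**3. Effect on a late switcher, by RNA status.**

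| Day 1 | At switch | Rule as written | Rule on reference value |
|---|---|---|---|
| below 50 | below 50 | kept | kept |
| 50 or more | 50 or more | removed | removed |
| below 50 | 50 or more | kept | removed |
| 50 or more | below 50 | removed | kept |

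The third row can feed the rebound count, because SAP 4.6.1 counts confirmed values at or above threshold from the reference onwards.

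**4. Whether the third row can occur.** Entry to the extension requires adequate viral load results (SAP 1.2), with no number attached. Protocol 9.1.4 foresees control subjects at 50 or more both at Week 48 and at the retest who attend Week 52 and give a further sample. SAP 2.7.1 provides a reference category of 50 or more for late switchers. The documents thus allow for the case but give no count.

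**5. Size.** The planned control arm is 367, which caps the late-switch group. One subject is 1/367 = 0.27 points, and slightly more with a smaller denominator.

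Illustration, on assumptions the documents do not supply: a share v of late switchers is at 50 or more at the switch and was suppressed on Day 1; rebound is 2% in the others and r in these. The per-protocol rate under the rule as written is (1 − v) × 2% + v × r.

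- v = 1% (367 × 0.01 = about 4 subjects), r = 30%: 0.99 × 2% + 0.01 × 30% = 2.28%.
- v = 4% (367 × 0.04 = about 15 subjects), r = 50%: 0.96 × 2% + 0.04 × 50% = 3.92%.

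With the exclusion on the reference value the rate would be 2.0% in both cases. Clopper-Pearson 95% intervals, with counts rounded to whole subjects, are 0.95% to 4.25% against 0.78% to 3.93% in the first case, and 2.10% to 6.32% against 0.80% to 4.05% in the second. They overlap throughout.

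**The case against.** **The switch was conditional on viral load.** Control subjects at 50 or more at Week 48 were to be retested within 3 weeks before switching (Time and Events Schedule), and Attachment 1 item 12 removes subjects whose value of 50 or more had no timely follow-up test. This stands in part: it should keep the numbers small. But the condition has no numeric limit, and item 12 catches a missing retest, not a documented value of 50 or more.

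**Switch status is examined elsewhere.** The reference viral-load subgroup, the subgroup by rebound in the first 48 weeks and the Cox term all bear on it. This also stands and lowers the consequence. It does not make the per-protocol set itself coherent.

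**The SAP follows the protocol.** Protocol 11.3 says baseline, and a late switcher at 50 or more at the switch may have committed no deviation. That is true, so the change must be declared as a departure. The RNA condition was, however, added because of the population of interest and sits alongside the deviation criterion, not within it.

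**Stronger readings that the documents do not support.** A reader might infer from the adherence sentence that late switchers are filtered on adherence to the wrong drug. They are not: the rule takes the worse of two periods, one of which is switch to Week 96, so adherence below 65% on D/C/F/TAF always excludes. The earlier period may exclude some subjects who later took D/C/F/TAF well, and the efficacy subgroup differs in using "Adherence based on D/C/F/TAF (i.e., from reference) drug accountability". But SAP 3.6 derives the two periods deliberately, Attachment 1 prescribes the worse of them for this group, and keeping out subjects with a year of poor adherence is defensible in a robustness set. A reader might also suppose that a large part of the Week 96 tables is affected. Late switchers are at most 367 of 734 + 367 = 1,101, one third. Safety is analysed on the ITT set (SAP 2.6.1), and per-protocol analysis covers only key secondary efficacy endpoints, with outputs left to the Data Presentation Specifications (SAP 4.6.2).

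**Conclusion.** The concern holds for the RNA exclusion. Attachment 1 applies it to late switchers at a time that matches neither their efficacy window nor the stated reason for the exclusion, and it can misplace subjects in both directions. The consequence is confined to the late-switch per-protocol outputs. The set is secondary (SAP 2.6.2), Week 96 carries no formal hypothesis (SAP 1.3) and efficacy results are descriptive (SAP 4.4.1), so no test, margin or power figure is touched.

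The firm size is 0.27 points or slightly more per misplaced subject. The range of 2.3% to 3.9% against 2.0% rests entirely on assumed inputs and shows only what could happen if 1% to 4% were at 50 or more at the switch. This is a minor point that is cheap to correct.

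**What to change.** In Attachment 1, keep the Day 1 rule for initial switchers. For the Late Switch group, state that subjects whose SAP 2.9 reference RNA (last value before the switch) is 50 copies/mL or more are excluded from the per-protocol set. Note this in the SAP as a departure from the baseline wording of Protocol 11.3, with the Amendment 4 rationale as the reason. Report how many late switchers change status in each direction, so that the effect is visible. Leave the adherence rule as it is.

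The cost is one or two sentences of SAP text and a change to one population flag. The reference value is already derived for the subgroup analyses, and no new data are needed. The change should be recorded before the Week 96 per-protocol outputs are produced.

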## 4.1. Inclusion Criteria

Each potential subject must satisfy all of the following criteria to be enrolled in the study.

- 1. The ability to understand and sign a written ICF, which must be obtained prior to initiation of study procedures.
- 2. Currently being treated with a stable ARV regimen consisting of a bPI (limited to DRV once daily with rtv or COBI, ATV with rtv or COBI, or LPV with rtv) combined with FTC/TDF only, for at least 6 consecutive months preceding the screening visit.

Subjects treated with the combination DRV + COBI + FTC/TDF and having completed the required visits in the GS-US-216-0130 study, and who are fulfilling the present protocol criteria, will be given the option to participate in this study.

Note: A change in pharmacokinetic booster (ie, rtv or COBI) will be allowed provided such a switch occurred no less than 1 month prior to the screening visit.

- 3. Documented evidence of being virologically suppressed while on a stable ARV regimen prior to screening: at least 1 plasma HIV-1 RNA measurement <50 copies/mL (or HIV-1 RNA undetectable by a local HIV-1 RNA test) occurring between 12 and 2 months prior to the screening visit while on the stable ARV regimen and have HIV-1 RNA <50 copies/mL at the screening visit.
  - A single viral load elevation of ≥50 copies/mL and <200 HIV-1 RNA copies/mL after previously reaching viral suppression ('blip') within 12 months prior to screening is allowed, provided a subsequent viral load measurement is <50 HIV-1 RNA copies/mL (or HIV-1 RNA undetectable by a local HIV-1 RNA test) prior to screening.
- 4. Screening eGFRcr  $\geq$ 50 mL/min according to the Cockcroft-Gault formula for creatinine clearance.
- 5. Absence of history of failure on DRV treatment and absence of DRV RAMs (including V11I, V32I, L33F, I47V, I50V, I54M, I54L, T74P, L76V, I84V, L89V), if documented historical genotypes are available.
  - If no historical genotype is available, the subject can be included, provided no previous failure on DRV treatment has been documented.
- 6. Normal ECG at screening (or if abnormal, determined by the investigator to be not clinically significant).
- 7. Screening hepatic transaminases (alanine aminotransferase [ALT] and AST) ≤5 x upper limit of the normal range (ULN).
- 8. Screening direct bilirubin  $\leq 1.5 \text{ x ULN}$ .
  - Subjects with documented Gilbert's Syndrome or hyperbilirubinemia due to ATV therapy may have total bilirubin up to 5 x ULN.

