2.6.2. Per Protocol Analysis Set

An analysis based on the per protocol (PP) population will also be performed to investigate the impact of excluding subjects with major protocol violations and to evaluate the robustness of the analysis results. The PP population will include all subjects who:

- (1) are randomized into the study,
- (2) have received ≥ 1 dose of treatment in the study, and
- (3) without any major protocol deviation that is considered to potentially affect efficacy outcomes. Specific details are provided in Attachment 1.

The PP analysis set is the secondary analysis set for efficacy analysis. The per protocol (PP) set is defined as the ITT analysis set minus subjects with major protocol violations as listed in Attachment 1.

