4.6.1. Definitions

Virologic Rebound

Virologic rebound is defined as:

- subjects who show confirmed HIV-1 RNA $\geq 50/20/200$ copies/mL from the reference up to, and including Week 96,
- subjects who discontinued prematurely (irrespective of reason) for which the last available (single) HIV-1 RNA value on treatment was $\geq 50/20/200$ copies/mL.
- any subject with last available on-treatment HIV-1 RNA $\geq 50/20/200$ copies/mL at the study cut-off of Week 96 (i.e., any last viral load [re]test having occurred no later than 6 weeks after Week 96)

All other situations are considered non-rebounders.

Snapshot approach (applying 20/50/200 copies/mL as threshold)

The Snapshot approach will classify subjects into 3 outcome categories: “virologic success”, “virologic failure” and “No viral load data”. Several subcategories of the outcome will also be presented in the analysis and are shown below. The categories below are mutually exclusive such that a subject will be included in one (sub)category. If a subject discontinues in the time window but also has an HIV-RNA value in the time window then the viral load data will be used to classify the subject’s category.

- Virologic success:
 - Last available HIV RNA $< 20/50/200$ copies/mL in the Week 96 visit window (Week 90-102)
- Virologic failure:
 - Last available HIV RNA $\geq 20/50/200$ copies/mL in the Week 96 visit window (Week 90-102)
 - Virologic failure leading to discontinuation

- Discontinued due to other reason (i.e. other than AE/death or virologic failure) and last available HIV-RNA $\geq 20/50/200$ copies/mL
- No viral load data in the Week 96 visit window
 - Discontinued due to AE/death (subjects will be classified in this category if discontinued prior to Week 96 window regardless of HIV-RNA level)
 - Discontinued due to other reason (i.e. other than AE/death or virologic failure) and the last available HIV RNA $< 20/50/200$ copies/mL (or missing)
 - Missing data during the Week 96 visit window but on study

The following threshold criteria are considered:

- < 20 : HIV RNA below 20 copies/mL (target not detected or target detected)
- < 50 : HIV RNA below 50 copies/mL
- < 200 : HIV-RNA below 200 copies/mL

Imputations for missing values

The following imputation method is used to calculate **virologic response** at a given time point:

- observed case: subjects with a missing value are disregarded in the analysis for that time point.

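### SAP Attachment 1 item 2 is wider than inclusion criterion 3: read as written, detectable local results below 50 copies/mL can count as an entry deviation and remove eligible subjects from the per-protocol set

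*SAP*

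**What the plan says.** Protocol section 4.1, criterion 3, asks for documented suppression before screening: "at least 1 plasma HIV-1 RNA measurement <50 copies/mL (or HIV-1 RNA undetectable by a local HIV-1 RNA test"), dated between 12 and 2 months before screening, together with a value below 50 at screening. Either alternative is enough. The same criterion restricts only real elevations: "A single viral load elevation of ≥50 copies/mL and <200 HIV-1 RNA copies/mL after previously reaching viral suppression" is allowed within 12 months of screening, provided a later value before screening is below 50 or locally undetectable. SAP section 1.2 repeats these rules.

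SAP Attachment 1 item 2 turns the criterion into a deviation. It lists five alternative conditions, any one of which is enough:

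1. no result below 50 (or locally undetectable) in the 12-to-2-month window;
2. any result of 200 or more;
3. "The subject has documented more than 1 plasma HIV-1 RNA concentrations" of 50 copies/mL or more, with the bracketed addition "or HIV-1 RNA detectable by a local" test;
4. a result from 50 to below 200 with no later value below 50 by two months before screening;
5. a screening value of 50 or more.

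The item carries the coded term for subjects who entered without meeting criteria and is marked Yes for exclusion. The attachment's introduction says that "if such deviations are reported for a subject, the subject will be excluded from the PP analysis". Item 9, on disallowed medication, provides for adjudication; item 2 does not.

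SAP section 2.6.2 gives the role of the set: "The PP analysis set is the secondary analysis set for efficacy analysis".

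**The concern.** Being detectable and being at or above 50 copies/mL are different things. A sensitive assay can report a number between 20 and 49, or a detected result below 20. Criterion 3 treats such results as suppressed. The bracket in condition 3 puts them on the same footing as a result of 50 or more, without saying which local assays or report formats it is meant for.

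Two outputs depend on this. The PP set, on which SAP section 4.6.2 repeats the key secondary endpoints as a robustness check, would lose subjects who belong to the population the trial set out to study. The tabulation of major deviations by arm (SAP section 3.8) would describe subjects as failing an entry criterion that they met. In both, the outcome would turn on how sensitive the local assay was, not on eligibility.

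**Working it through.** The plan gives no figure on this point, so there is nothing to reproduce. The check compares two rules.

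**Logic.** Under criterion 3 a result is suppressed if it is (below 50) OR (locally undetectable). The negation is (50 or more) AND (locally detectable). Condition 3 joins the two parts with OR, so it takes in results that are detectable but below 50.

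**Consistency within item 2.** Condition 1 accepts any value below 50 as suppression. Condition 4 accepts a later value below 50 as resolving a blip and does not ask whether it was detectable. A subject with two local results of 30 passes condition 1 and is caught by condition 3. A subject with a blip of 120 followed by 30 passes condition 4 and is also caught by condition 3.

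**Consistency with the rest of the SAP.** The Snapshot definitions in section 4.6.1 put "target not detected or target detected" together in the below-20 category, and section 4.4.2 scores both kinds of below-20 result at 19. These rules govern on-study central-laboratory results, so they show how the SAP treats detection elsewhere. They do not show what local assays reported before screening.

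**Enumeration.** Take two local results in time order, both within the 12-to-2-month window, with a screening value below 50 assumed. Each result is one of eight: undetectable, 19, 30, 49, 50, 120, 199 or 250 copies/mL, all but the first being detectable. That gives 8 × 8 = 64 ordered pairs.

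| Pair | Number | Criterion 3 | Condition 3 as written | Bracket removed |
|---|---|---|---|---|
| Both suppressed, at least one undetectable | 4 × 4 − 3 × 3 = 7 | eligible | not flagged | not flagged |
| Both detectable and below 50 | 3 × 3 = 9 | eligible | flagged | not flagged |
| Blip (50, 120, 199), then undetectable | 3 × 1 = 3 | eligible | not flagged | not flagged |
| Blip, then detectable below 50 | 3 × 3 = 9 | eligible | flagged | not flagged |
| All other pairs | 64 − 28 = 36 | not eligible | not relevant here | not relevant here |

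Eligible pairs: 7 + 9 + 3 + 9 = 28. Eligible but flagged as written: 9 + 9 = 18. Eligible but flagged with the bracket removed, or limited to results that cannot be read as below 50: 0.

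The 18 is a count of patterns on a chosen grid. It shows that the mismatch exists and which histories trigger it. It says nothing about how common those histories are.

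**The case against.** The best defence is that the literal reading cannot be what the drafters meant. Because it conflicts with conditions 1 and 4 of the same item, the bracket is more sensibly taken as the mirror of the protocol's allowance for locally undetectable results, meant for local reports not expressed against 50 copies/mL. That is plausible, but the SAP does not say it, and the correction below keeps exactly that use.

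A second argument is that exclusion follows only if the deviation is reported. A site or monitor would have to report a subject as failing a criterion that was met, under a Protocol Deviation Criteria document that is not among the documents available. This stands: it is not shown that any subject was in fact excluded this way. It does not make the written rule correct.

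Third, dependence on the local assay is not peculiar to the SAP, since criterion 3 also accepts a locally undetectable result with no stated limit. That is true. But there it can only help a subject to qualify; in condition 3 it can disqualify a subject whose values are all below 50.

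Fourth, changing the rule now could make PP membership differ from the Week 48 analysis if the same item was used there. That SAP is not available. The risk is real, and reporting the change deals with it.

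**Conclusion.** The point holds as a mismatch between a stated rule and the criterion it enforces. Two history patterns are affected: two detectable results below 50, and one permitted blip with a detectable value below 50. A single detectable result below 50, with nothing else, does not trigger condition 3.

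The consequences are limited. This SAP covers Week 96 only, tests no hypothesis (section 1.3) and reports efficacy descriptively (section 4.4.1). The ITT set is untouched, and the Week 48 noninferiority analysis is not described here (section 4.5.1). What is affected is membership of the secondary PP set and the deviation tabulation.

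A reader might infer more: that a sizeable share of subjects is lost, or that the PP rebound rate is pushed downward because those removed are more likely to rebound. The documents support neither. They give no frequency of local testing before screening, no probability of a detectable result below 50 and no description of the local assays, so any percentage would come from assumed inputs. Nor do they show that detectable values below 50 predict rebound. The number of subjects affected and the direction of any bias are undetermined.

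The conclusion assumes that the attachment is applied as written and that the Protocol Deviation Criteria document does not already narrow the bracket.

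**What to change.** In SAP Attachment 1 item 2, third condition, count only results of 50 copies/mL or more. Let a locally detectable result count only where the local assay cannot show a value below 50 and no number was reported. State that detectable results below 50 are not deviations. Make the same change in the Protocol Deviation Criteria document if it carries the same wording.

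Apply the corrected rule to both the deviation listing and the PP flag, and report any subject whose PP status differs from the Week 48 analysis.

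The cost is a sentence in each document and a re-derivation of the flag from recorded pre-screening results. The documents do not say whether local values were captured as numbers. Where only detected or not detected was recorded, the assay's limit would have to be looked up. No subjects were recruited after the Week 48 analysis (SAP section 3.4), so the review covers a closed set of subjects and needs no new data from them.
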